At the end of the study, a research assistant will also debrief the participant about the purpose of the study, and conduct an exit interview to determine how comfortable the participant felt answering the questions and to learn what did and did not work well. As part of the exit interview, for participants that are 45 years of age or older, we will ask a short battery of questions about colon cancer screening and then all participants will be presented with a small set of questions to get detailed feedback from individuals on how they understood certain questions, what type of response format they prefer, and what was or was not confusing. These colon cancer screening questions relate to the Meaning and Purpose questionnaire that is already embedded in our study as individuals who report greater meaning and purpose are more motivated to engage in their healthcare and improve their overall health and wellbeing and are more likely to participant in preventive health services,

including colonoscopies, etc. Based on screening recommendations from the American Cancer Society, we will be asking these additional questions to participants that are 45 years of age or older to determine if participants are adherent to the recommended screening timeframes. According to the guidelines from the United States Preventive Services Task Force and the American Cancer Society. Participants are classified as adherent if they reported receipt of either a FOBT within 1 year, colonoscopy within 10 years, sigmoidoscopy within 5 years, or both a colonoscopy and sigmoidoscopy within 10 years. We will then relate participant's adherence to their answers to the Meaning and Purpose questionnaire.

Research procedures and activities for phone-based protocol:

Due to the COVID-19 pandemic, the study will implement phone-based assessments in addition to the original in-person protocol. A research team member will contact enrolled or previously enrolled participants to give more information about the phone-based protocol and to assess interest. If a participant is interested, they will be verbally consented over the phone. Each of the three phone sessions will last approximately 60 minutes. At each phone-based visit, the participant will respond to the following questionnaires via phone-based administration:

- 1. PROMIS-29
- 2. NIH Toolbox Meaning and Purpose
- 3. Colorectal Cancer Screening Questions (at one time-point, if not already completed at an in-person visit)

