After completing the questionnaires, research coordinators will debrief with participants by asking questions to determine if the questionnaires missed any important factors of how participants are currently feeling. Debriefing will happen at the end of each call. During the debriefing participants will be asked a few questions about how easy/difficult the questions were for them to answer, an open-ended qualitative question, "We've just asked you some questions about your health over the past 7 days, thank you for answering those questions. Is there anything else about your health that we didn't ask you about over the past 7 days that you think is important to tell us?" and a 1-item rating scale adapted from FDA Global Impression of Change Rating Scale, "Please choose the response that best describes the overall change in your health since your last study visit" with response options of "much better, a little better, no change, a little worse, much worse".

4.4 Monitoring of participant safety: This study involves the completion of questionnaires and literacy tests. As far as we know from our extensive experience with these tests, there are no psychological or physical risks. We will be asking questions about depression and anxiety. Thus, after each assessment, the research coordinator will review these questionnaires to determine whether significant depression or anxiety is present. All participants will be given a referral list at the end of each study visit in case the need ever arises for him or her to seek mental health treatment.

All research team members will be trained to assess suicidality using C-SSRS, a state-of-the-art and widely used suicide assessment tool. If any participant endorses suicidality on the PHQ-9, the research assistant/coordinator will notify any licensed psychologist or physician on the research team, either in person or via text page. Then the participant will be screened using the C-SSRS for further assessment. If the licensed psychologist/physician is immediately available they will assess the participant. If a licensed psychologist/physician is not immediately available, the research assistant/coordinator will begin the C-SSRS

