assessment until the licensed psychologist/physician can arrive. Suicide prevention steps will be taken in the unlikely event that a participant has active suicidal intentions; these procedures include taking the participant to the Northwestern Medicine Emergency Department or notifying emergency services by calling 911.

During the phone-based protocol, the PHQ-9 questions will not be asked and no other questions that address suicidality are present in the phone-based protocol. During the informed consent process, the research coordinator will tell participants that if they appear to be a risk to themselves or others, the coordinator will call 911 to request emergency services. In the unlikely event that emergency services do need to be requested, the research coordinator will ask all participants their current location at the beginning of each call so that information is available for potential emergency service response. If the participant does not appear to be an imminent threat to themselves or others but would like mental health resources, we will email or mail (depending on participant preference) a copy of the mental health resource list to them.

4.5 Study Timeline. We anticipate recruitment of participants to begin March of 2018, preceded by a brief pilot-testing phase to ensure all procedures run smoothly. We aim to recruit 17 participants per month for three years to reach our local (i.e., Northwestern) target of *N* = 612. Each participant will be invited to complete a baseline (i.e., visit 1), three-month (i.e., visit 2), and six-month (i.e., visit 3) follow-up assessment. The first visit will take between 120-150 minutes and the second and third visits will last 60-90 minutes each. Recruitment for the phone-based protocol is anticipated to begin in July of 2020. Phone-based visits are expected to take approximately 60 minutes. We aim to enroll all 612 participants from the in-person protocol for the phone-based protocol. Each participant in the phone-based protocol will be asked to complete a baseline assessment (visit 1), three-month assessment (visit 2), and six-month assessment (visit 3). These 3 time-points are separate from their inperson visits. The final year of the project will be used for data analysis, manuscript writing, and study close-out.

4.6 Types of assessments completed.

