Authorized representatives of the National Institutes of Health (NIH), as well as authorized members of the IRBs, will have also have access to study records.

There are no specimens associated with this study.

15.0 Data Monitoring Plan to Ensure the Safety of Participants:

We are asking questions about depression and anxiety, for which good treatments exists. As such, we will give all participants a referral list for possible mental health treatment, with information letting them know that they can contact us at any time for additional help finding a referral. Giving this information to all participants ensures that no person will be missed, and also reduces any feelings of stigma that might arise if the person felt singled out based on their responses. As described above, we will monitor the suicidality item of the PHQ-9 at each and every visit. Based on the PHQ-9, the coordinator will follow up as needed with the C-SSRS to assess whether additional assessment and/or intervention are needed. The C-SSRS will serve as the report form to document this additional information. For any participant with moderate or greater risk, a licensed psychologist or physician on the research team will talk to the participant to gather more information and make appropriate recommendations and referrals. As described above, any immediate suicidal intent will be treated as a life threatening emergency. We will take the person to the Emergency Department or involve emergency services from 911 if needed.

16.0 Data and if applicable, Specimen Banking:

No Biosample Storage and Shipment will be used

17.0 Qualifications to Conduct Research and Resources Available:

Our team includes the PI, a licensed clinical psychologist with extensive experience delivering psychotherapy as well as in health-related research. We also have licensed internists on the team. Our team has extensive experience working with patients across a variety of settings. Additionally, our research coordinators have graduate degrees and extensive experience interpreting and translating documents from English to Spanish.

No additional psychological or medical resources should be needed as a result of this study. If further needs should arise, however, the study PI will assist the participant in getting connected with appropriate follow-up care. All participants will be given a referral list at the end of the study.

References

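### Protocol 15.0 promises PHQ-9 suicidality monitoring at every visit, but 4.4 omits it at the three phone visits and gives no explicit phone route to a clinician for non-imminent suicidal thoughts

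*Protocol*

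**What the plan says.** Section 15.0, the safety monitoring plan, says: "As described above, we will monitor the suicidality item of the PHQ-9 at each and every visit". It continues: "Based on the PHQ-9, the coordinator will follow up as needed with the C-SSRS". It then provides that a licensed psychologist or physician on the team will talk to any participant whose risk is moderate or greater.

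Section 4.4 sets the working procedure. For a PHQ-9 endorsement it says: "If any participant endorses suicidality on the PHQ-9, the research assistant/coordinator will notify any licensed psychologist or physician on the research team". The notification is made in person or by text page, and the C-SSRS follows.

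For the phone sessions, 4.4 says that "the PHQ-9 questions will not be asked and no other questions that address suicidality are present in the phone-based protocol". Its phone paragraph then provides three things:

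- Participants are told at consent that "if they appear to be a risk to themselves or others, the coordinator will call 911 to request emergency services".
- Their location is taken at the start of each call.
- A resource list is emailed or mailed under this condition: "If the participant does not appear to be an imminent threat to themselves or others but would like mental health resources".

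Section 4.3 calls the phone sessions visits: "At each phone-based visit, the participant will respond to the following questionnaires via phone-based administration". Each call ends with a debriefing that includes an open question on whether anything else about the participant's health is important to tell the study.

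**The concern.** Section 15.0 is where an ethics board or a new coordinator would look for the safety plan. Read by itself, it says that every visit carries a suicidality check. Half of the planned visits of someone in both protocols do not.

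The wording also has a practical side. In person, an endorsement on the PHQ-9 leads by a written step to a licensed clinician. On a call that starting point does not exist, yet a participant can still voice suicidal thoughts. The open debriefing question makes this foreseeable, and taking the location on each call shows that the authors had emergencies in mind. The case left without an explicit instruction is the one short of an emergency: thoughts are voiced, 911 is not called, and someone qualified should follow up. What is at stake is clear conduct by the coordinator and timely clinical contact. No estimate or test in the SAP depends on it.

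**Working it through.** There is no figure in the plan to reproduce. The check compares the texts, with a few simple counts.

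1. **Are the phone sessions visits?** Yes. Sections 4.3 and 4.5 both use that word for them. Section 3.0 requires willingness for three in-person and three phone sessions, so a participant in both has 3 + 3 = 6 visits.

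2. **Is the PHQ-9 asked by phone?** The phone battery in 4.3 has three parts: the PROMIS-29, the NIH Toolbox Meaning and Purpose scale, and the colorectal screening questions at one time point. The PHQ-9 is not among them, and 4.4 says so outright. The item is asked at 0 of 3 phone visits. The 15.0 sentence implies 6 of 6 visits; the procedures give at most 3 of 6.

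3. **Does the opening of the 15.0 sentence rescue it?** It refers back to what was described above. What stands above, in 4.4, includes the phone exception. The cross-reference leads a careful reader to the right rule but does not make the sentence true.

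4. **Where does the written route to a clinician start?** The notification in 4.4 starts from a PHQ-9 endorsement. The C-SSRS step in 15.0 is based on the PHQ-9. The footnote to the visit table in 4.3 gives the C-SSRS only to those who endorse suicidality on the PHQ-9, though that table is for in-person visits. The clinician sentence in 15.0 is general, but no phone procedure is written that would grade a participant as moderate or greater risk.

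5. **Does the phone paragraph supply its own route?** The in-person text of 4.4 mentions a licensed psychologist or physician four times, all within one notification step. The phone paragraph mentions one zero times.

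6. **Do the general provisions fill the gap?** These are not limited to in-person visits:
   - Coordinators review the questionnaires for significant depression or anxiety after each assessment (4.4). No clinician contact is attached to that review.
   - All team members are trained in the C-SSRS (4.4).
   - The team can discuss distress and refer if the participant wishes (10.0).
   - Participants may contact the team at any time for help with a referral (15.0).
   - The PI, a licensed clinical psychologist, helps connect participants to care if needs arise (17.0).

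   Together they make clinician involvement possible and even likely. None tells a coordinator on a call when to start it.

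**The case against.** The best defence is that 15.0 merely contains stale wording. Section 4.4 states the exception openly, the specific rule governs the general one, and nobody can monitor an item that is not in the battery. This stands in large part: nothing is concealed, and the sentence alone changes no conduct.

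The second defence is that a clinician step exists. The 15.0 provision for moderate or greater risk has no in-person limit, staff are trained to assess risk, and the PI is a licensed psychologist. This also stands as mitigation. It leaves the phone route implied where the in-person route is spelled out.

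Three stronger readings are tempting, and the documents do not support them.

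- A reader might infer that a coordinator must choose between 911 and a mailed list. The text does not present these as the only options, and nothing forbids paging a clinician.
- A reader might infer that the two phone triggers conflict dangerously, since one speaks of a risk and the other of an imminent threat. They can overlap, but the overlap favours the 911 call, which is the protective direction. The first trigger also reports what is said at consent, and the consent pages are not in the file.
- A reader might infer that phone participants lose the referral list. Section 4.4 says: "All participants will be given a referral list at the end of each study visit", and 15.0 also promises it to all. Phone participants come from the in-person cohort, so the phone sentence can be read as offering a further copy.

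**Conclusion.** The point holds as a minor one. The 15.0 sentence is untrue for 3 of 3 phone visits, and the plan has no explicit phone route to a licensed clinician for suicidal thoughts that do not lead to a 911 call. Emergencies are covered, and the general provisions reduce the gap without closing it.

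The counts describe the text and do not measure harm. The documents give no basis for estimating how often suicidal thoughts are voiced on a call. The conclusion assumes that the phone consent script and call instructions, which are not in the file, do not already contain a clinician step. The reviewed protocol is dated 13 July 2020, the month in which phone recruitment was expected to begin. The SAP was updated well after that, so the practical benefit depends on calls still to be made or on reuse of the text.

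**What to change.** Two changes of wording.

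1. In 15.0, replace the monitoring sentence with: *At each in-person visit the PHQ-9 suicidality item is monitored. The PHQ-9 is not asked at phone visits; section 4.4 gives the phone procedure.*

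2. In the phone paragraph of 4.4, keep the present 911 wording and add: *If a participant voices suicidal thoughts and 911 is not called, or if the coordinator is unsure of the risk, the coordinator notifies a licensed psychologist or physician on the team by text page during or directly after the call. That clinician phones the participant to learn more and to make recommendations and referrals.*

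The second change uses the paging route already in 4.4. It sends uncertain cases to a clinician and does not lower the present 911 protection. No suicidality question is added, and the resource list arrangements can stay as they are.

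The cost is a short amendment with matching call instructions, and an occasional call by clinicians already on the team. Questionnaires and analyses do not change.

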In recent years, the NIH has invested heavily in the creation of the Patient-Reported Outcomes Measurement Information System (PROMIS),⁷⁻¹³ which is a large collection of state-of-the-art questionnaires designed to measure symptoms and other health-related concepts. PROMIS has advanced health measurement and the ability to incorporate patients' perspectives into clinical decision-making. But PROMIS, like almost all other questionnaires, has not been validated for use by people with low health literacy, and may work poorly for individuals with low levels of health literacy. Thus, people with low literacy may be inaccurately assessed in all research and clinical settings due to unrecognized measurement bias of commonly used tools. The goal of this study is to determine how health literacy affects selected PROMIS and other questionnaires, so that these tools can be improved, resulting in precise health assessment for all participants.

At the time of this version of the analysis plan (Version 5.0), several modifications have been made to the protocol and analysis plan in response to the COVID-19 pandemic. Interim analyses of the data, before data was complete included 1) a trial run of downloading the data from REDCap and merging constituent files, 2) exploratory analyses of cognition (measured by the MOCA-B) and PROMIS Depression, and 3) exploratory analyses of screening data (Single Item Literacy Screener, demographics) as a predictor of health literacy; these latter analyses were done to help better stratify our participants. All analyses that were not pre-registered will be labelled as post-hoc, exploratory analyses. This document is meant to supplement the detailed study protocol and focuses on the analytic methodology. The goal of this document is to describe *a priori* statistical and methodological decisions, which will be adhered to rigorously through the analysis process.

Study Objectives

Using a large sample, we will determine the psychometric properties of health questionnaires across levels of health literacy. Testing will be conducted in English and Spanish, across two modes of administration (paper-and-pencil vs. talking touchscreen). Each participant will have three visits (baseline, 3-month, and 6-month follow-up), described below, in order to determine changes in psychometric properties over time. We will use *differential item functioning* (DIF) and other psychometric analyses to identify questionnaire items with varying characteristics across levels of health literacy. Before the COVID-19 pandemic, our original plan was to recruit $N = 1216$ participants for in-person assessments. At the time of this plan our final N is 728 participants who have completed a health literacy assessment; some of these participants are missing data on subsequent questionnaires. In-person recruitment was put on hold during the COVID-19 pandemic; in order to adapt the the pandemic, a subset of participants ($N = 304$) was invited to a phone-based protocol that included data collection about the impact of COVID-19, vaccine confidence, and health-related quality-of-life (PROMIS-29 profile).

- **Develop alternative modes of test administration that can better accommodate people with low health literacy.** National statistics indicate that 14% of adults in the United States have below basic reading skills, and over 75 million Americans have below basic or basic health literacy skills.¹⁴ These data strongly indicate that many individuals seeking health care will have difficulties with written questionnaires, even those that have been carefully developed such as those in the NIH PROMIS. We will test an alternative mode of administration that has been specifically designed to aid people of low health literacy – a computer-assisted “talking” version that uses speech technology that participants can privately access as needed to have items and response options

read to them. We will analyze the talking touchscreen groups and paper-based groups separately. We hypothesize that the talking touchscreen will reduce health literacy-related test bias by level of health literacy, relative to traditional paper-based methods. This will be evidenced by fewer items being flagged for DIF in the group that receives the talking touchscreen. In terms of descriptive statistics to display the magnitude of effects, we will report effect sizes (McFadden's R^2) of DIF items, as well as test characteristic curves (TCCs) for DIF items. Among participants with low health literacy, we expect that the discrimination parameters of the touchscreen condition will be higher than the paper-based condition.

- **Determine the degree of differential item functioning (DIF) of tools relevant to clinical research across different levels of health literacy.** DIF analyses will be conducted to identify test bias by level of health literacy. This will ensure that individuals with low literacy are assessed fairly in clinical and research settings. We will assess a broadly applicable instrument to primary care – the PROMIS Profile, which measures anxiety, depression, fatigue, pain interference, pain intensity, physical function, sleep disturbance, and social roles and activities. Other questionnaires included in the study are shown in Table 1. We will stratify participants into low versus adequate literacy levels using Health LiTT (groups will be formed according to T scores of < 55 vs. 55+).¹⁵ A secondary analysis will use the NUMI, a measure of health numeracy, in three groups (low = 0-3, medium = 4-6, high = 7 or greater). Then, we will determine whether psychometric properties of each questionnaire scale are consistent for individuals with low health literacy versus adequate health literacy. We hypothesize that DIF will be observed for multiple scales using paper-and-pencil administration, suggesting a need to improve test items, and a need to examine alternative ways to administer these tools.

Statistical methodology

Overview

Data will be summarized by group and in total. In summary tables of continuous variables, the minimum, maximum, mean, and standard deviation will be presented with one decimal place. We will use counts and percentages in table for categorical variables. The denominator for each percentage will be the number of participants within the group unless otherwise specified. All hypothesis testing will be carried out at a two-tailed Type I error rate of $\alpha = .05$ unless otherwise specified. P-values will be rounded to three decimal places with a minimum of < 0.001 in tables. If statistical methods change during analysis, this will be documented in all reports with justification. Additional analyses of these data will be inevitable, but any exploratory analyses will be clearly marked as such.

Statistical power analysis and sample size selection

IRT and DIF analyses require large samples due to the large number of free parameters to be estimated. The proposed sample size herein is larger than other successful implementations of these same analyses carried out in other IRT studies.¹⁶⁻¹⁹ Moreover, we have carried out computer simulations to determine if our proposed sample sizes will be sufficient to create IRT models. We assumed a one-factor model across two groups at $n = 100$ each with standardized factor loadings set to .7 for eight questionnaire items. We used two groups for this simulation to ensure that any pairwise model comparisons would have adequate power. For this simulation, we specified that a non-significant model χ^2 was a good fit, which is a conservative decision because this particular test is highly sensitive relative to other measures of model fit, especially with large samples. Across 500 iterations, a good-fitting model was identified across groups 90% of the time. Even dropping the sample size to as low as $n = 50$ would identify a good-fitting model 84% of the time.

Missing data

We will describe the rate of missing data on an item-by-item basis using frequency tables in R. We do not anticipate high rates of missing data, but we will conduct subgroup analyses by health literacy, site, and administration mode as need to help diagnose any problems with missing data. For DIF analyses, IRT models

Table 1	
Visit 1 (Baseline)	Description of instrument
Language Assessment	To determine testing in English or Spanish
Single Item Health Literacy Screener	To screen for possible literacy status
Short Portable Mental Status Questionnaire (SPMSQ)	To determine cognitive status to ensure the possible participant has sufficient mental status to participate
Demographics	To assess participant characteristics
Health Literacy Assessment (Health LiTT)	Assessment of health literacy.
NUMI	Assessment of numeracy. That is, how well the person can process numerical information
PROMIS Profile	To assess health-related quality of life.
PHQ-9	Self-report measure of depression.
Berlin Questionnaire (for sleep)	Self-report measure of sleep quality
Purpose and Meaning (NIH Toolbox)	Self-report measure of the degree of meaning and purpose a person feels in their life.
Ruminative Responses Scale (RRS)	Self-report measure of negative, repetitive thoughts
PTSD Checklist	Self-report measure of posttraumatic stress disorder symptoms
* C-SSRS Lifetime	Self-report measure of recent history of suicidal ideation and behavior. (This is not a variable of interest that will be used only to ensure patients' safety).
*C-SSRS Last Contact	Self-report measure of suicidal ideation and behavior since the individual's most recent assessment. (Used only as necessary to ensure patients' safety).
Visit 1, but if missing at Visit 1, then given at Visit 2 or 3	
Screening tools for Alzheimer's disease and related dementias (ADRD)	This brief battery contains the Montreal Cognitive Assessment-Basic (MOCA-B), and selected items from the RUDAS. * Note: These items were added to the study after recruitment began, so we give them at Visit 1, but if they were not given at Visit 1, they are then administered at Visit 2 or 3
Visit 2 (3-months)	
PROMIS Profile	To assess health-related quality of life
PHQ-9	Self-report measure of depression
Berlin Questionnaire (for sleep)	Self-report measure of sleep quality
Purpose and Meaning (NIH Toolbox)	Self-report measure of the degree of meaning and purpose a person feels in their life.
RRS	Self-report measure of negative, repetitive thoughts.
PTSD Checklist	Self-report measure of posttraumatic stress disorder symptoms.
*C-SSRS Lifetime	Self-report measure of recent history of suicidal ideation and behavior. (This is not a variable of interest that will be used only to ensure patients' safety).
*C-SSRS Last Contact	Self-report measure of suicidal ideation and behavior since the individual's most recent assessment. (Used only as necessary to ensure patients' safety).
Visit 3 (6-months)	
PROMIS Profile	To assess health-related quality of life.
PHQ-9	Self-report measure of depression.
Berlin Questionnaire (for sleep)	Self-report measure of sleep quality.
Purpose and Meaning (NIH Toolbox)	Self-report measure of the degree of meaning and purpose a person feels in their life.
RRS	Self-report measure of negative, repetitive thoughts.
PTSD Checklist	Self-report measure of posttraumatic stress disorder symptoms.
*C-SSRS Lifetime	Self-report measure of recent history of suicidal ideation and behavior. (This is not a variable of interest that will be used only to ensure patients' safety).
*C-SSRS Last Contact	Self-report measure of suicidal ideation and behavior since the individual's most recent assessment. (Used only as necessary to ensure patients' safety).
Exit Interview	

are estimated using full-information approaches that use all available data and can accommodate missing responses. We do not foresee a need for an imputation strategy, but if that were to become necessary, we will update this plan accordingly before running any analyses.

Study Design

This is a randomized experiment aimed at determining whether talking touchscreen technology can reduce DIF and provide a better testing experience, relative to paper-based testing. The original study design is shown below in Table 2, although as a result of the COVID-19 pandemic, we were unable to recruit all 1216 participants, but instead collected additional longitudinal data on a subset of participants ($n = 304$)

Table 2: Study Design			
Northwestern		BUMC	
304 English speaking 152 with low health literacy 76 women g1 38 randomized to paper-based 19 Order 1 19 Order 2 38 randomized to talking touchscreen 19 Order 1 19 Order 2 76 men g2 38 randomized to paper-based 19 Order 1 19 Order 2 38 randomized to talking touchscreen 19 Order 1 19 Order 2 152 with adequate health literacy 76 women g3 38 randomized to paper-based 19 Order 1 19 Order 2 38 randomized talking touchscreen 19 Order 1 19 Order 2 76 men g4 38 randomized to paper-based 19 Order 1 19 Order 2 38 randomized talking touchscreen 19 Order 1 19 Order 2	304 Spanish speaking 152 with low health literacy 76 women g5 38 randomized to paper-based 19 Order 1 19 Order 2 38 randomized to talking touchscreen 19 Order 1 19 Order 2 76 men g6 38 randomized to paper-based 19 Order 1 19 Order 2 38 randomized to talking touchscreen 19 Order 1 19 Order 2 152 with adequate health literacy 76 women g7 38 randomized to paper-based 19 Order 1 19 Order 2 38 randomized talking touchscreen 19 Order 1 19 Order 2 76 men g8 38 randomized to paper-based 19 Order 1 19 Order 2 38 randomized talking touchscreen 19 Order 1 19 Order 2	304 English speaking 152 with low health literacy 76 women g9 38 randomized to paper-based 19 Order 1 19 Order 2 38 randomized to talking touchscreen 19 Order 1 19 Order 2 76 men g10 38 randomized to paper-based 19 Order 1 19 Order 2 38 randomized to talking touchscreen 19 Order 1 19 Order 2 152 with adequate health literacy 76 women g11 38 randomized to paper-based 19 Order 1 19 Order 2 38 randomized to talking touchscreen 19 Order 1 19 Order 2 76 men g12 38 randomized to paper-based 19 Order 1 19 Order 2 38 randomized to talking touchscreen 19 Order 1 19 Order 2	304 Spanish speaking 152 with low health literacy 76 women g13 38 randomized to paper-based 19 Order 1 19 Order 2 38 randomized to talking touchscreen 19 Order 1 19 Order 2 76 men g14 38 randomized to paper-based 19 Order 1 19 Order 2 38 randomized to talking touchscreen 19 Order 1 19 Order 2 152 with adequate health literacy 76 women g15 38 randomized to paper-based 19 Order 1 19 Order 2 38 randomized to talking touchscreen 19 Order 1 19 Order 2 76 men g16 38 randomized to paper-based 19 Order 1 19 Order 2 38 randomized to talking touchscreen 19 Order 1 19 Order 2

Study Timepoints

Each participant will be asked to complete a baseline assessment (Visit 1), three-month follow-up (Visit 2), and a six-month follow-up (Visit 3). Longitudinal data will be analyzed, within language and within mode of administration (paper-based vs. talking touchscreen), on a scale-by-scale basis using multiple-group factor analysis to compare in Mplus software (see Table 3 schematic below). All items will be treated as categorical indicators with response categories collapsed if there are fewer than five responses for a given response option.

Table 3: Schematic of multiple-group confirmatory factor analysis to be used on a scale-by-scale basis			
	Visit 1	Visit 2	Visit 3
Adequate health literacy	Factor loadings/ IRT parameters	Factor loadings/ IRT parameters	Factor loadings/ IRT parameters
Low health literacy	Factor loadings/ IRT parameters	Factor loadings/ IRT parameters	Factor loadings/ IRT parameters

We hypothesize that a metric invariable model will fit well for the talking touchscreen method. Acceptable fit will be defined as $CFI \geq .90$, $TLI \geq .90$, and $RMSEA \leq .10$. We hypothesize that unacceptable fit indices will be obtained for the paper-based testing. For descriptive statistics, we will report all fit indices produced by Mplus as well as factor loadings for each item. Longitudinal data will also be used to develop new longitudinal DIF tools in R, but these results will be considered exploratory until they can be tried and tested in other data sets.

Study Populations

The study population includes medical patients and community member, all might which complete questionnaires in other clinical and research contexts, ages 18 and older.

Study Variables

Demographics

All demographic variables are described in the protocol. We will report descriptive statistics of all demographics within language group as well as in total. We do not have specific hypotheses about demographics, but may conduct and report analyses of them, as well as presented additional analyses of demographics based on requests from manuscript reviewers.

Health literacy and numeracy

HealthLiTT and the NUMI will be used to determine health literacy groups using the above-described cutoffs. HealthLiTT is our main health literacy variable. All analyses of the NUMI are secondary.

Health questionnaires

The following questionnaires will be subjected to DIF analyses: the PROMIS Profile (physical function, anxiety, depression, fatigue, sleep disturbance, ability to participate in social roles and activities, and pain interference), the Berlin Questionnaire (for sleep), the NIH Toolbox scale for purpose and meaning, the PTSD checklist (20 symptom items assessing overall PTSD symptoms), the Ruminative Responses Scale (total score and brooding and reflection subscales), and the PHQ-9.

Screening tools for Alzheimer's disease and related dementias (ADRD)

Based on supplemental funding, a brief battery of screening tools for ADRD was added to the project. These screening tools include the Montreal Cognitive Assessment Test-Basic (MOCA-B),²⁰ the Visuospatial/Executive, Attention, and Language subtests of the MOCA 8.1,²¹ and the Body Orientation, Fist/Palm, Judgement, and Language Generativity – Animal Naming subtests of the Rowland universal dementia assessment scale.²² The first participant completed the ADRD screening tools on 10 July 2019. These tools are given at the baseline visit, but if the baseline visit has already occurred, the tools are given at one of the follow-up visits (Visit 2 or Visit 3).

Interim analyses to ensure data quality

In order to ensure data integrity and quality, we will conduct limited interim data analyses after 150 patients have enrolled. The goal of this analysis will be to conduct a “dry run” of data management procedures. We will import, merge, clean, and examine the data quality. Merging is necessary because data will be collected from multiple sites using different data collection platforms. Data merging will require uniformity of file format, data variable names, and the value coding within each variable. Once merged, we will examine the data for any out-of-range, non-numerical, unexpected or missing values that may represent technological or experimental errors. We will also compose statistical software syntax based on existing scoring rules; these rules will name and define composite variables at the questionnaire (scale) score level. Health variables will be correlated and examined to confirm the correct coding of the variables (e.g., re-coding of responses or reversing). We will document these data management steps and produce software syntax necessary for successful merger, any challenges encountered, and remedies we put in place. The overarching goal of these interim analyses are to prepare for the analyses of the final data set.

Primary analyses

DIF by health literacy

